9.10 Analysis of Standard MR Sequences

To compare the methods of MRI sequence, the response categories (complete response, partial response, stable disease, and progression) will be determined from the following three standard MR sequences, T2-weighted, FLAIR, T1-weighted post-contrast. Percent agreement between the sequences will be estimated as the number of follow-up scans in which the corresponding sequence agreed divided by the total number of follow-up scans. Standard error will be estimated by use of the bootstrap method²⁸ to account for the correlated dependent response data, and these values will be used to estimate the 95% confidence intervals. The event-free survival distributions will be compared across the MR sequences, with a proportional hazards model developed for dependent survival data by Wei et al (1989).²⁹

9.11 Effect of the Stratification on Response Rate

At enrollment, the number of prior therapies, classified as 2 or fewer versus more than 2 will be required to complete the treatment assignment process. The efficacy rule described in [Section 9.5](#) will be executed as written regardless of the number of prior therapies that a patient has received. The risk for EFS-event and death associated with receiving more than 2 prior regimens will be assessed using the stratified 1-sided log-rank test, with randomized regimen as the stratification factor. Only patients enrolled after approval of the proposed amendment will be considered in the analysis. If the resulting p-value is not significant at the 0.10 level or less, the EFS and OS results will be presented without regard to stratification factor.

The following logistic regression model will be utilized:

$$\Pr(CR \text{ or } PR | \underline{x}_i) = \frac{e^{x_i \beta}}{1 + e^{x_i \beta}};$$

where: x_{i1} is 1

x_{i2} is the random treatment assignment

x_{i3} is 1 if the patient received three or more prior regimens and 0 otherwise

The value and p-value associated with the estimate of β_3 will be used to infer whether there is evidence of an association between response rate and number of prior regimens

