3.1.6 Randomization

Randomization will take place at the time a patient is entered On Study via eRDE. Patients will be assigned to receive one of two lenalidomide doses with equal probability: 20 mg/m²/day (Regimen A – low dose) or 115 mg/m²/day (Regimen B – high dose). Patients will be stratified according to the number of prior regimens (2 or less regimens versus greater than 2 regimens).

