9.4 Analysis of Efficacy

A total of 74 eligible patients will be enrolled on this trial. Patients will be randomly assigned to either the low dose (Regimen A) or the high dose arm (Regimen B). Each patient will be classified according to their 'best response' for the purposes of analysis of treatment effect. Best response is determined from the sequence of the objective statuses described in [Section 10.0](#) 'Response Criteria.' A responder is defined as a patient who achieves a best overall response of CR or PR at any time on the study. If a patient achieves a PR or CR and later has progressive disease or relapse, then the patient will be counted as a responder. The response rate will be calculated as the ratio of the number of patients who demonstrate response (CR or PR) divided by the number of patients evaluable for response. The 95% confidence bounds for response rate are shown in the table below for several different outcomes. The computation is based on the binomial distribution, assuming the availability of 30 evaluable patients (7 inevaluable patients) for response in each arm (each dose level). All patients eligible for study who receive any study drug will be considered evaluable for response. Any patient who goes off protocol therapy for any reason (patient/parent/physician choice, adverse event profile, etc.) prior to the first response evaluation will be considered a non-responder. For example, an observed response rate of 33% (10/30) will be consistent with the view that 17% or more patients will respond to the treatment.

Outcome (#Response/#Patients)	95% Exact Confidence Bound on Response Rate
20/30	(0.47, 0.83)
15/30	(0.31, 0.69)
10/30	(0.17, 0.53)
5/30	(0.06, 0.35)

There would be modest power to compare the response rates for the 2 dose cohorts. With 74 patients, we would have 80% power to detect a response rate difference of 35% vs. 15%, at the 1-sided 20% significance level.

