Disease progression will be based on the results of institutional review. Standard survival methods will be used for analysis of EFS and OS. Analyses include log rank tests and the product-limit (Kaplan-Meier) estimate for estimation of EFS and OS probability. Comparison of EFS between the two dose levels will primarily be exploratory. With 74 patients, we will have only approximately 69% power to detect a 15% increase in long-term EFS (30% to 45%) with 50% patients receiving high dose vs. 50% receiving low dose, based on a one-sided logrank test with 20% Type I error rate.

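### Randomisation is stratified by number of prior regimens, but the dose log-rank tests in 9.4 name no strata, and 9.11 lets a 0.10-level pre-test decide whether the factor is set aside

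*Combined protocol and SAP*

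**What the plan says.** - **Randomisation (3.1.6).** Allocation is 1:1. "Patients will be stratified according to the number of prior regimens", in two classes: 2 or fewer, and more than 2.
- **EFS and OS (9.4).** "Analyses include log rank tests and the product-limit (Kaplan-Meier) estimate for estimation of EFS and OS probability". No strata are mentioned. The EFS power statement (about 69% for long-term EFS of 30% against 45%, 74 patients) is "based on a one-sided logrank test with 20% Type I error rate". The section adds: "Comparison of EFS between the two dose levels will primarily be exploratory".
- **Prior-regimen effect (9.11).** A stratified one-sided log-rank test is planned, but it tests the effect of having had more than 2 prior regimens, with dose arm as the stratum. It is limited to patients enrolled after an amendment. "If the resulting p-value is not significant at the 0.10 level or less", then "the EFS and OS results will be presented without regard to stratification factor". The other outcome has no rule.
- **Response (9.4 and 9.11).** With 74 patients, "we would have 80% power to detect a response rate difference of 35% vs. 15%, at the 1-sided 20% significance level". No test is named. The logistic model in 9.11 contains both dose and prior-regimen class, but the only inference stated for it concerns the prior-regimen coefficient.

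**The concern.** The usual rule is to analyse by the factor used to randomise. Here the dose comparison reads as unstratified, although the plan does not use that word. Whether the factor enters the presentation of EFS and OS depends on a significance test in part of the data. Failure to reach 0.10 in such a small trial is weak evidence that the factor does not matter. If the test is significant, the analyst must choose afterwards between a stratified test, an adjusted model and separate curves.

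A reader may think that 9.11 already fills the gap, because it contains a stratified log-rank test and a logistic model with a dose term. The first tests a different hypothesis, and the second states no inference on dose.

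At stake are a little precision in the EFS comparison, and freedom to choose the EFS and response analyses after seeing the data.

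**Working it through.** **1. The plan's EFS figure.** Inputs from 9.4: 37 per arm, 30% against 45%, one-sided 0.20.

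- Hazard ratio = ln(0.45)/ln(0.30) = 0.663.
- Events, assuming everyone is followed to the long-term level: 37 × 0.70 + 37 × 0.55 = 46.25. The plan states no event count.
- Schoenfeld power = Φ(½ × √46.25 × |ln 0.663| − 0.842) = Φ(1.396 − 0.842) = 0.71.
- A fixed-time difference in proportions gives 0.690.

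The stated 69% therefore stands. Neither calculation uses strata.

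**2. Stratified against unstratified dose log-rank.** This was simulated with proportional hazards, marginal long-term EFS of 30% and 45%, 37 per arm and 40,000 trials per scenario. The documents give no stratum share, stratum effect or post-amendment share. The assumptions were 30% or 50% with more than 2 regimens, and 25% to 100% enrolled post-amendment. Post-amendment patients were randomised in pairs within stratum and earlier patients in pairs ignoring it, so chance imbalance is included.

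| Assumed stratum HR | Power, stratified minus unstratified (points) |
|---|---|
| 1 | −0.5 to −0.2 |
| 1.5 | 0 to +0.4 |
| 2 | +1.1 to +2.0 |
| 3 | +3.8 to +5.1 |

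Unstratified size is 0.19 to 0.20 at HR 2 and 0.18 to 0.20 at HR 3; stratified size is 0.20 to 0.205. A separate run with equal, balanced strata gave −0.2, +1.4 and +4.2 points at HR 1, 2 and 3.

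Two variations:

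- If an arm closes at 20 patients under 9.5, the difference is −0.8 to +0.4 up to HR 1.5, and +0.8 to +1.7 at HR 2.
- If half of the earlier patients have no recorded count and form their own stratum, it is −0.9 to −0.2 with no effect, and +0.3 to +1.4 at HR 2.

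**3. The plan's response figure.** Inputs from 9.4: 35% against 15%, one-sided 0.20, 37 per arm.

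- Null SE = √(2 × 0.25 × 0.75/37) = 0.1007.
- Alternative SE = √((0.35 × 0.65 + 0.15 × 0.85)/37) = 0.0980.
- Uncorrected: Φ((0.20 − 0.842 × 0.1007)/0.0980) = 0.88.
- With continuity correction, subtracting 1/37 from the difference: 0.816.

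Full enumeration of the two binomials gives:

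| Test | Power, 37 per arm | Power, 30 per arm | True size, 37 per arm (common rate 15% to 25%) |
|---|---|---|---|
| Pooled z | 0.879 | 0.850 | 0.19 to 0.21 |
| Fisher's exact | 0.821 | 0.772 | about 0.13 |

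At 37 per arm both meet the stated 80%. The 6-point gap is largely a difference in true size.

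**4. Size at low response rates.** Section 9.5 treats a 5% response rate as inadequate, so size matters there too. At 37 per arm, ignoring early closure, an unadjusted likelihood-ratio dose test has size of about 0.24 at 5% and 0.22 at 10%. Pooled z also has 0.24 at 5%; Fisher's has 0.08. At 5%, an arm has no responders with probability 0.95^37 = 0.150, so at least one arm has none with probability 1 − (1 − 0.150)² = 0.28. The usual odds ratio and its interval then fail.

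**The case against.** The strongest reply is that no planned decision depends on this. The primary objective is the response rate under each regimen, and 9.4 reports it with exact bounds per arm. The go/no-go rule in 9.5 is applied per arm, and 9.11 says it runs whatever the number of prior therapies. The EFS comparison is labelled primarily exploratory and the response comparison is described as having modest power. The stratum effects are assumed. The gate governs presentation, and one sentence could complete it. If its unwritten branch means using the stratified test, the result stays within 1.5 points of always stratifying. All of this stands, and it keeps the point minor. It does not supply the missing branch or a reason to leave the randomisation factor to a pre-test. The exploratory label also covers EFS only, while the protocol summary calls the study a randomised comparison of response rate.

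Four stronger readings are tempting, and the documents do not support them:

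- **Ignoring the strata inflates the error rate.** It does the reverse: the unstratified test is slightly conservative.
- **The stated 80% for response is wrong.** At 37 per arm it is met by both tests. The interval table in 9.4 does assume 30 evaluable per arm, where Fisher's gives 0.77. But 9.4 also says "All patients eligible for study who receive any study drug will be considered evaluable for response", which points to a number nearer 37.
- **The post-amendment restriction also shrinks the logistic model.** The restriction follows the log-rank test and leads into that test's p-value; the model is introduced separately afterwards. The natural reading leaves the model unrestricted.
- **Earlier patients were randomised without the factor.** The restriction suggests this, but the plan does not say so.

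**Conclusion.** The point holds as a minor gap in specification. The dose log-rank tests name no strata although randomisation is stratified, and a one-branched 0.10-level pre-test in post-amendment patients decides whether EFS and OS are shown without the factor. Stratifying costs about 0.5 point of power or less if the factor is not prognostic and gains about 1 to 2 points at a stratum hazard ratio of 2. The gain depends on assumed stratum shares, stratum effects and post-amendment shares; the textual gap does not.

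The unnamed response test is secondary. It is mostly missing detail, because both candidates reach the stated power at 37 per arm. It still deserves naming, because the candidates differ in true size (about 0.20 against 0.13), and pooled z and the likelihood-ratio test exceed 0.20 at the low response rates that 9.5 guards against.

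**What to change.** 1. **Section 9.4, EFS and OS.** State that EFS will be compared between regimens by a one-sided log-rank test at the 20% level, stratified by number of prior regimens (2 or fewer versus more than 2), in all eligible randomised patients, and that any OS comparison will use the same strata. For earlier patients, take the stratum from baseline treatment history. Place those with no recorded count in a separate *unknown* stratum.
2. **Section 9.11.** Delete the 0.10 gate. Keep the prior-regimen test as descriptive, and say that the post-amendment restriction applies to that test only.
3. **Response comparison (secondary).** Name one test in advance that holds its size at low response rates, in all patients evaluable for response under 9.4. An example is an exact test stratified by prior regimens, that is, exact conditional inference on the dose coefficient of the 9.11 model. Do not use the likelihood-ratio test without a small-count fallback. Compute the power of the chosen test before adopting it; the 0.82 above is for the unstratified Fisher's test.

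**Cost.** SAP wording, plus abstraction of prior-regimen counts for earlier patients, whose number the documents do not give. If the factor is not prognostic, EFS power falls by about 0.5 point at most with complete counts, and by up to 0.9 point if half of the earlier patients fall in the unknown stratum. The sample size and the 9.5 rule do not change.

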9.12 Gender and Minority Accrual Estimates

Both males and females of all races and ethnic groups are eligible for this study. The gender and minority distribution of the study population is expected to be:

Accrual Targets			
Ethnic Category	Sex/Gender		
	Females	Males	Total
Hispanic or Latino	2	1	3
Not Hispanic or Latino	37	40	77
Ethnic Category: Total of all subjects	39	41	80
Racial Category			
American Indian or Alaskan Native	1	0	1
Asian	1	1	2
Black or African American	4	3	7
Native Hawaiian or other Pacific Islander	1	1	2
White	32	36	68
Racial Category: Total of all subjects	39	41	80

This distribution was derived from CCG 9891/POG 9130.

10.0 EVALUATION CRITERIA

10.1 Common Terminology Criteria for Adverse Events (CTCAE)

This study will utilize version 4.0 of the CTCAE of the National Cancer Institute (NCI) for toxicity and performance reporting. A copy of the CTCAE version 4.0 can be downloaded from the CTEP website (http://ctep.cancer.gov/protocolDevelopment/electronic_applications/ctc.htm).

Please note: 'CTCAE v4.0' is understood to represent the most current version of CTCAE v4.0 as referenced on the CTEP website (ie, v4.02 and all subsequent iterations prior to version 5.0).

[figure not shown]
10.2 Methodology to Determine Tumor Measurement

Tumor dimensions are determined by measurement of the longest tumor dimension and its perpendicular for each target lesion. Regarding MRI imaging, the radiologist at each institution may select whatever sequence best highlights the tumor (T1 enhanced or T2

weighted or FLAIR images) and the same sequence should be used for serial measurements. Response determination will be based on a comparison of an area (W x T – see below) between the baseline assessment and the study date designated in the follow-up Report Form. Reports for the follow-up exams should reiterate the measurements obtained at baseline for each target lesion. Non-target lesions or newly occurring lesions should also be enumerated in these reports, and changes in non-target lesions should be described.

Tumor response criteria are determined by changes in size using the longest tumor dimension, and its perpendicular. Either T1 or T2 weighted images are used - which ever gives the best estimate of tumor size. The following section describes the methodology. (See Figure 10.1 below for illustration)

1. For MRI imaging (preferred), the longest diameter can be measured from the axial plane or the plane in which the tumor is best seen or measured, provided the same plane is used in follow ups. This longest measurement of the tumor is referred to as the width (W). Longest diameter of target lesion(s) should be selected in the axial plane only for CT.
2. The perpendicular measurements should be determined - transverse (T) measurement, perpendicular to the width in the selected plane.
3. The cystic or necrotic components of a tumor are not considered in tumor measurements. Therefore only the solid component of cystic/necrotic tumors should be measured. If cysts/necrosis composes the majority of the lesion, the lesion may not be "measurable".
Options:
 - if the cyst/necrosis is eccentric, the W and T of the solid portion should be measured, the cyst/necrosis excluded from measurement
 - if the cyst/necrosis is central but represents a small portion of the tumor (< 25%), disregard and measure the whole lesion
 - if the cyst/necrosis is central but represents a large portion of the tumor, identify a solid aspect of the mass that can be reproducibly measured
4. Leptomeningeal tumor spread is usually not a target lesion, and usually cannot be measured accurately. Presence and location of leptomeningeal tumor spread should be noted and change in extent/thickness assessed on follow up studies.

Figure 10.1: COG Guidelines for Measurement of Tumor Size

5. Overall Response Assessment

The overall response assessment takes into account response in both the target and non-target lesion, and the appearance of new lesions, where applicable, according to the criteria described in the table below. The overall response assessment is shown in the last column, and depends on the assessments of target, non-target, and new lesions in the preceding columns.

Target Lesions	Non-target Lesions	New Lesions	Overall Response
CR	CR	No	CR
CR	IR/SD	No	PR
PR	CR, IR/SD	No	PR
SD	CR, IR/SD	No	SD
PD	Any	Yes or No	PD
Any	PD	Yes or No	PD
Any	Any	Yes	PD

CR – Complete Response

PR – Partial Response

SD – Stable Disease

PD – Progressive Disease

IR – Incomplete Response

The sections that follow discuss the selection and evaluation of each of these types of lesions.

10.3 Selection of Target and Non-Target Lesions

1. For most CNS tumors, only one lesion/mass is present and therefore is considered a “target” for measurement/follow up to assess for tumor progression/response.
2. If multiple measurable lesions are present, up to 3 should be selected as “target” lesions. Target lesions should be selected on the basis of size and suitability for accurate repeated measurements. All other lesions will be followed as non-target lesions (including CSF positive for tumor cells).
3. The lower size limit of the target lesion(s) should be at least twice the thickness of the slices showing the tumor to decrease the partial volume effect (e.g. 8 mm lesion for a 4 mm slice).
4. Any change in size of non-target lesions should be noted, though does not need to be measured.

10.4 Response Criteria for Target Lesions

1. Response criteria are assessed in 2 dimensions – the product of W x T.
2. To assess response/progression, the ratio is calculated:

$$\frac{W \times T \text{ (current scan)}}{W \times T \text{ (reference scan)}}$$

3. Development of new disease or progression in any established lesions is considered progressive disease, regardless of response in other lesions – e.g. when multiple lesions show opposite responses, the progressive disease takes precedence.
4. For purposes of this study, response criteria for target lesions are:

Complete Response (CR): Complete disappearance of all known disease for at least 4 weeks. Complete response is dated from the time all lesions have disappeared.

Partial response (PR): A reduction of at least 50% in the size of all measurable tumor as quantitated by the sum of the products of the largest diameters of measurable lesions and maintained for at least 4 weeks. Partial response is dated from the time of first observation. In addition, there can be no appearance of new lesions or progression of any lesion.

Stable Disease (SD): A decrease of <50% or an increase of <25% in the sum of the products of the largest diameters of measurable lesions and no evidence of new lesions.

Progressive Disease (PD): $\geq 25\%$ increase in the sum of the products of the largest diameters of the measurable lesions or the appearance of one or more new lesions. Two-dimensional measurements (using WHO criteria) of an existing tumor will be compared to the study baseline or best response scan (whichever is smaller) compared side-by-side.

Local progression is defined as progression of known residual tumor or the appearance of tumor at known prior sites of disease that were at some point without evidence of disease. Distant progression is defined as the appearance of tumor at sites other than known prior sites of disease. Distant progression most often occurs in the subarachnoid space and may occur at any point within the neuraxis. Although rare, extra-CNS metastasis represents distant failure. Combined local and distant progression is defined when evaluation of the entire neuraxis reveals local and distant progression.

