3.2.3.3 Brain and Spine MRI

To document the degree of residual tumor, the following must be obtained (see [Section 14.0](#) for complete details):

3.2.3.3.1

All patients must have a brain MRI with and without contrast (gadolinium) within 1 week prior to study enrollment. For patients on steroids, baseline MRI scans must be performed after at least 1 week at a stable or decreasing dose of steroids.

3.2.3.3.2

All patients with a history of spinal or leptomeningeal disease, and those patients with symptoms suspicious of spinal disease, must have a spine MRI with and without contrast (gadolinium) performed within 2 weeks prior to study enrollment.

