3.2.6 Concomitant Medications Restrictions

(Please see [Section 4.2](#) for the concomitant therapy restrictions for patients during treatment.)

- a. Growth factor(s): Must not have received within 2 weeks of entry onto this study.
- b. Steroids: Patients who are receiving corticosteroids must be on a stable or decreasing dose for at least 1 week prior to baseline MRI.

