4.2 Concomitant therapy restrictions

4.2.1

Concurrent cancer therapy, including chemotherapy, radiation therapy, immunotherapy, or biologic therapy may NOT be administered to patients while on this study. The use of alternative or complementary therapies is discouraged.

4.2.2

Radiotherapy is not permitted.

4.2.3

Filgrastim (G-CSF) may be used at the treating physician's discretion in patients with severe neutropenia (i.e. ANC <500/ μ L) to enhance neutrophil recovery when clinically indicated (for culture proven bacteremia or invasive fungal infections). Prophylactic or routine use of filgrastim in clinically well patients awaiting count recovery is not recommended.

4.2.4

Corticosteroid therapy is permissible only for the treatment of increased intracranial pressure or physiologic replacement. The lowest dose consistent with good medical management should be used. Corticosteroids should NOT be used as an antiemetic due to their effect on the blood brain barrier. Patients on steroids who require an increase in steroid dose for worsening neurologic symptoms should have an MRI performed within 72 hours to rule out tumor progression.

4.2.5

Appropriate antibiotics, blood products, antiemetics, fluids, electrolytes and general supportive care are to be used as necessary. Antiemetics should not be given prophylactically for cycle 1.

4.2.6

Anticonvulsants may be administered as clinically indicated. However, it is unclear what effect, if any, lenalidomide has on anticonvulsant pharmacokinetics. It is strongly recommended that anticonvulsant levels be checked at least weekly during the first course of therapy.

4.2.7

Drugs known to be pro-thrombotic (i.e. erythropoietic stimulating agents) should be avoided.

For COG Supportive Care Guidelines see:

https://members.childrensoncologygroup.org/prot/reference_materials.asp under Standard Sections for Protocols.

4.3

Lenalidomide Administration

The lenalidomide cycle will be repeated every 28 days. Each cycle will be comprised of lenalidomide orally once daily for 21 days followed by 7 days without lenalidomide. Lenalidomide should be taken at approximately the same time each day. One cycle of lenalidomide is described below. **Lenalinomide is distributed by the NCI DTCD. Do not use commercially available drug.**

Begin Cycle 1 on Day 1 if ANC \geq 1,000/ μ L, platelet count \geq 100,000/ μ L (transfusion independent), and upon the following:

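### Corticosteroid dose is controlled for the baseline MRI but not for the follow-up MRIs that score CR and PR, so shrinkage on a raised dose counts as a response.

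*Combined protocol and SAP*

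**What the plan says.** **Baseline.** Section 3.2.3.3.1 states: "For patients on steroids, baseline MRI scans must be performed after at least 1 week at a stable or decreasing dose of steroids". Section 3.2.6b repeats it: "Patients who are receiving corticosteroids must be on a stable or decreasing dose for at least 1 week prior to baseline MRI". Section 4.1 carries the same condition in its description of the baseline scan.

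**On study.** Section 4.2.4 keeps steroids available within limits: "Corticosteroid therapy is permissible only for the treatment of increased intracranial pressure or physiologic replacement". It asks for the lowest dose consistent with good management and bars antiemetic use: "Corticosteroids should NOT be used as an antiemetic due to their effect on the blood brain barrier". Its only link between an on-study dose change and imaging is this: "Patients on steroids who require an increase in steroid dose for worsening neurologic symptoms should have an MRI performed within 72 hours", for the purpose of ruling out progression.

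**Scoring.** In Section 10.2, "Response determination will be based on a comparison of an area" between baseline and the follow-up date. Section 10.4 defines PR as "A reduction of at least 50% in the size of all measurable tumor as quantitated by the sum of the products of the largest diameters", maintained for at least 4 weeks, with no new or progressing lesion. CR is disappearance of all disease for at least 4 weeks. Section 14.3 takes the baseline MRI as the comparator for response and the smallest product since the start of treatment as the comparator for progression. Section 9.4 counts a patient as a responder if CR or PR is reached at any time, even if progression follows. None of these sections mentions steroid dose. It is also absent from the 7.1 evaluation table and from the list of material for central review in 14.4.

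**The concern.** Response is a ratio of two areas. The protocol controls steroid dose for the denominator (the baseline scan) and not for the numerator (the follow-up scan). Having made a stable or falling dose a condition of a valid baseline image, it lets a follow-up image on a higher dose be read as drug effect.

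Objective response is the primary endpoint, and the two-stage rule in Section 9.5 turns on small counts. A regimen needs at least 2 responders in 20 to continue and at least 4 in 37 to be judged worth pursuing. One patient misread as a responder moves the observed rate by 1/37 = 2.7 percentage points. Because response at any time counts, the misreading is permanent.

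**Working it through.** **1. Where a steroid condition appears.**

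| Element | Section | Steroid condition? |
|---|---|---|
| Baseline MRI | 3.2.3.3.1, 3.2.6b, 4.1 | Yes |
| Follow-up MRI schedule | 4.1, 7.1, 14.1 | No |
| Measurement and overall response table | 10.2 | No |
| CR, PR, SD, PD definitions | 10.4 | No |
| Comparison with baseline | 14.3 | No |
| Responder definition | 9.4 | No |
| Central review submission | 14.4 | No |

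**2. Does the 4-week rule remove the problem?** Scheduled MRIs fall before cycles 3, 5, 7 and so on, so they are 2 × 28 = 56 days apart through cycle 13 and 3 × 28 = 84 days apart later. The rule removes brief shrinkage. It does not remove shrinkage that lasts while the raised dose continues, because both scans can be taken on that dose.

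**3. Reproduce the Section 9.5 design.** Each patient is a responder (probability r), an early progression (p) or neither (1 − r − p). Stage I counts (R1, P1) are trinomial with n = 20, and the stage II additions (R2, P2) are trinomial with n = 17.

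- Continue if R1 ≥ 2 and P1 ≤ 9.
- Accept if the trial continues and R1 + R2 ≥ 4 and P1 + P2 ≤ 14.

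Exact enumeration gives:

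| r | p | Stop at stage I: printed / recomputed | Accept: printed / recomputed |
|---|---|---|---|
| 0.05 | 0.40 | 0.78 / 0.778 | 0.05 / 0.054 |
| 0.10 | 0.40 | 0.51 / 0.505 | 0.24 / 0.237 |
| 0.20 | 0.30 | 0.11 / 0.108 | 0.81 / 0.806 |
| 0.15 | 0.25 | 0.18 / 0.184 | 0.73 / 0.732 |
| 0.20 | 0.25 | 0.08 / 0.080 | 0.88 / 0.884 |

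All five rows agree within rounding.

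**4. Add false responses.** Take the protocol's inadequate regimen (r = 0.05, p = 0.40). Let a further share m of patients be scored CR or PR through steroid effect, all of whom would otherwise be stable. The scored rates become r = 0.05 + m and p = 0.40. The documents give no value for m, so these are assumptions:

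| m | Scored r | Probability of accepting the regimen |
|---|---|---|
| 0 | 0.050 | 0.054 |
| 1% | 0.060 | 0.086 |
| 2.7% (1 in 37) | 0.077 | 0.149 |
| 5% | 0.100 | 0.237 |

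The last row is the protocol's own printed row for 10% response and 40% progression.

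Section 9.5 looks at the first 6 months, so only false responses arising in that window act on this decision. Later ones still enter the Section 9.4 response rate.

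**The case against.** The strongest reply is that few patients will be affected. Steroids are limited to two indications at the lowest adequate dose. Section 14.2 says these tumors are usually measured on FLAIR or T2, and 10.2 keeps the same sequence throughout. The blood-brain-barrier remark concerns antiemetics and does not mention imaging. Nothing in the documents shows steroids halving the solid-tumor area, and on the routine schedule the reduction would have to last about 8 weeks. This all stands. It limits the likely size of the problem but does not change what the rule counts as a response.

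Four stronger readings are tempting, and the documents do not support them:

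- **Steroids hide progression and so favor the drug on both counts.** PD is measured from the smallest scan, so an area lowered by steroids can make later regrowth count as PD, against the drug. The 72-hour MRI in 4.2.4 is also aimed at masked progression. It is partial: it covers patients already on steroids with worsening neurologic symptoms, and it does not alter how scans are scored. The net direction for progression is undetermined.
- **Affected cases can never be identified.** Section 7.1 does not list steroid dose, but the case report forms are posted elsewhere (12.0) and are not in the documents. What they collect on medication is unknown.
- **The bias differs between the two doses.** No document suggests different steroid use by arm, and antiemetic use is barred.
- **The protocol contradicts itself.** It does not. Size-only criteria are a design choice, and the point is that this choice leaves the primary endpoint open to bias.

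**Conclusion.** The point holds for CR and PR. The baseline image has a steroid condition, the follow-up image has none, and a reduction of at least 50% held for at least 4 weeks on a dose above baseline is a response as written. For the responder count the bias has one direction: a raised dose can add responders and cannot remove them. For progression no direction can be claimed.

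The size is unknown. False responses in 1% to 5% of patients would take the chance of accepting an inadequate regimen from 0.05 to between 0.09 and 0.24. That range rests on assumed misclassification rates, on false responders being drawn from stable disease, and on true rates of 5% and 40%. Reproducing the Section 9.5 table validates the calculation, not the steroid effect. If no patient is misclassified, the figure stays at 0.05. The change is worth making because the decision rests on so few responders and the remedy is cheap.

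**What to change.** **Sections 10.4 and 14.3.** State that a scan supports CR or PR only if the corticosteroid dose, other than physiologic replacement, is no higher than at the baseline scan and has been stable or decreasing for at least 1 week. Apply this to the first observation and to the later scan showing that the response has lasted at least 4 weeks. Otherwise score the scan as SD. PD by measurement still counts.

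**SD definition in 10.4.** Add a matching exception. SD is now limited to a decrease below 50%, so a larger decrease on a raised dose would otherwise have no category.

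**Data.** Record corticosteroid dose at each response MRI in the 7.1 table and on the response form, and send it to central review under 14.4.

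This changes endpoint scoring and data capture only. It leaves steroid use, sample size and the 9.5 boundaries as they are. It does not address masked progression. The cost is a short addition to the response sections and one data field. A few patients may move from PR to SD, so the reported response rate may be slightly lower.
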